7.10. Feedback Mechanism

Evaluation and response to any subject complaints will be reviewed by the DSMB. The IRB will be notified of protocols violations and emergence of unexpected AEs at any time during the study. In addition, a report by the DSMB will be provided to the IRB at the end of the study.

Table 1. Schedule of Study Procedures.

Period	Screen	Treatment Period 1			Assessment 1 ^{ab}	Treatment Period 2			Assessment 2 ^b
Visit	-1	1	2-9	10	11	12	13-20	21	22
Visit window	-3 months	-3 months	+1 month	+1 month	±1 month	-3 months	+1 month	+1 month	±1 month
Informed Consent	X								
Inclusion/Exclusion Criteria	X								
Demographics	X								
Medical History	X								
MRI Safety Screening	X					X			
Language Battery	X ^j		X ^{fh}		X	X ⁱ		X ^{fh}	X
Training Tasks		X	X	X	X	X	X	X	X
fMRI ^c		X ^g		X ^h		X ⁱ		X ^h	
MEG		X ^g		X ^h		X ⁱ		X ^h	
Randomization		X							
tDCS		X	X	X		X	X	X	
Phone Follow Up/					X				

Visit Reminder ^d									
Adverse Events ^d		X	X	X	X	X	X	X	X
TMS Neuronavigation (for stimulation planning) ^e	X ^j								

^a Assessment 1, Visit 11 occurs in the middle of the 16-week washout period.

^b In the case of early termination, Assessment Visit procedures will be performed.

^c Subjects will undergo mock scanner training. If a subject has been previously engaged in MRI as part of research, the subject may be excused from mock scanner training.

^d Phone Follow-Ups will be conducted during the 16-week washout period. They will be conducted 4 weeks post Treatment Period 1, 1 week prior to Assessment Visit 1, and 1 week prior to Treatment Period 2. AE review will be completed, and reminders for upcoming visits provided.

^e TMS Neuronavigation will occur at the investigators discretion.

^f Language assessment sessions will be conducted after Treatment periods 1 and 2 (visit 10 for period 1 and visit 21 for period 2).

^g These procedures can occur on 2 or more separate days, but within 3 months before the first treatment session of Treatment Period 1. They may overlap with Visit -1 procedures.

^h These procedures can occur on 2 or more separate days, but within 1 month after the last treatment session of Treatment Period 1 or the last treatment session of Treatment Period 2.

ⁱ These procedures can occur on 2 or more separate days, but within 3 months before the first treatment session of Treatment Period 2.

Study Title: High-Definition Transcranial Direct Current Stimulation (HD-tDCS) in logopenic variant Primary Progressive Aphasia (lvPPA): Effects on Language and Neural Mechanisms.

NCT: NCT03805659

Date of document: July 06, 2023

Statistical Analysis:

- The small sample size in this study precluded group-level statistical analysis.
- Instead focused on a within subject item-level analysis.
- Language performances in each trial period were assessed separately to help control for potential carryover effects and for effects of progressive neurodegeneration.
- The Cochran's Q test was used to determine if there were any differences on a dichotomous variable across the three-trial period timepoints.
- Because the same assessment list/version was used within a given stimulation condition per participant, we coded "right" and "wrong" answers to an individual assessment item as our dichotomous variable.
- If the preliminary Cochran's Q test demonstrated a significant difference ($p<0.05$) between participant responses in a language assessment between two timepoints, a follow-up non-parametric pairwise comparison between the baseline and timepoint list was tested using a McNemar test with a false discovery rate correction (Sheppard et al., 2021; Hung et al., 2017; Tsapkini et al., 2015).
- While the Cochran's Q and post-hoc McNemar test allowed us an objective comparison between timepoints within conditions for each individual participant, we utilized a Wilcoxon-signed rank test to assess participant performance changes between aHD-tDCS and sHD-tDCS (ex: aHD-tDCS T0-T1 percentage change from baseline vs. sHD-tDCS T0-T1 percentage change from baseline). This assessment would allow us a more quantitative direct comparison between treatment conditions on an individual participant (Sheppard et al., 2021). The statistical analyses described were performed using SPSS version 27.0 (IBM, Armonk NY). A p-value of <0.05 was used to describe statistical significance.

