6. DATA MANAGEMENT

6.1. A secure web-based system will be used to enroll patients and obtain the randomly assigned treatment group. Data forms will be printed, completed, and entered into the database using a secure web-based application. The database will be monitored for completeness, consistency, accuracy, and timeliness. No patient-identifying information will be stored in the database. To ensure that data are secure from external violation, computer systems containing study data will be password protected, and physical access to the computer systems will be limited.

6.2. Determination of changes in Language Function and Concurrent Improvement in Network Activity.

The language and MRI/rfMRI datasets will be obtained at baseline (before sham/active tDCS administration) and on the last day of each 2-week treatment period. These two time points will be denoted $t = 1, 2$. The two 10-

subject groups, both of which will receive both sham and active tDCS at different treatment phase, will be denoted $g = 1, 2$. The set of Language (LG) scores for subject s , from group g , at time t will be denoted $LG(s, g, t)$, where $s = 1, \dots, 10$; $g = 1, 2$; and $t = 1, 2$. The Language-Network functional connectivity (LFC) calculated between the left posterior temporal and inferior parietal cortex for subject s , from group g , at time t will be denoted $LFC(s, g, t)$.

6.3. Language Changes Due to Stimulation. Scores across all tests within the language battery will be combined into one composite measure to facilitate assessment of overall language performance across domains. All seven scores will be normalized to a Z-score by transforming individual raw test scores according to the mean and standard deviation of the scores for all subjects. Then, Z-scores of each test will be averaged to obtain an individual composite language Z-score (McConahey et al., 2017). We will employ age, years of education, gender, and gray matter (GM) volume as time-invariant covariates to obtain residual variables to determine the LG changes due to stimulation. We will model the LG score as a function of these nuisance regressors. This regression will be performed using all the data (i.e., all subjects, all groups, and all times):

$$\Delta LG(s, g, t) = \beta_0 + \beta_1 Age(s) + \beta_2 Edu(s) + \beta_3 GM(s) + \beta_4 Gender(s) + Res(s, g, t)$$

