7.8. Efficacy

Given the pilot nature of this study, two feasibility outcomes will be included: Consent rate and treatment completion rate. Only four patients are sufficient to calculate a 90% exact binomial confidence interval of (.56, 1) if all four are observed to complete treatment. Thus, this sample size would be large enough to potentially exclude completion rates of 56% or lower. The collection of pilot data from this study will provide initial estimates of the variability and the effect sizes. This information will then be used for the more formal calculations of power and sample size necessary to conduct a future trial.

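### The SAP, written once the sample was known, replaces the protocol's composite and group analysis with item-level tests and does not plan to report the effect-size and variability estimates the protocol names as a product of the pilot

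*SAP*

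**What the plan says.** Protocol section 6.3 sets the language endpoint. Scores across the battery "will be combined into one composite measure to facilitate assessment of overall language performance across domains", each test being converted to a Z-score and averaged. After regression on age, education, gender and gray matter volume, the residuals go into a crossed-nested ANOVA with group and time effects.

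Protocol section 7.8 states what the pilot is to yield: "The collection of pilot data from this study will provide initial estimates of the variability and the effect sizes". The next sentence assigns these estimates to power and sample-size calculations for a future trial. The Statistical Methodology row of the protocol summary repeats this, then adds that testing will use repeated-measures ANOVA once the sample is large enough.

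The SAP is headed "Date of document: July 06, 2023"; protocol version 5 is dated 26 May 2022. The SAP reports in the past tense: "The statistical analyses described were performed using SPSS version 27.0". It says "The small sample size in this study precluded group-level statistical analysis", and then "Instead focused on a within subject item-level analysis". The tests are Cochran's Q across three timepoints on items scored right or wrong, McNemar follow-ups with a false discovery rate correction, and an active-sham comparison: "we utilized a Wilcoxon-signed rank test to assess participant performance changes between aHD-tDCS and sHD-tDCS", described as "a more quantitative direct comparison between treatment conditions on an individual participant". The SAP does not give the number of participants analysed.

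**The concern.** The reason given for the change covers less than the change does. A small sample limits what a group test can show. It does not stop anyone computing a mean paired difference, its SD and an interval. The SAP treats the two as one and specifies neither.

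Item-level p-values within one participant describe that participant. They carry no between-participant variance, which is what a later trial needs for its sample size. Nor is the item-level plan a finer version of the composite: fluency counts and speech-rate measures (protocol section 5.4.4) are not naturally right/wrong items, so part of the planned endpoint has no obvious place in it.

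The past tense and the reference to the small sample show that this approach was settled with the sample known. Even so, the 0.05 threshold is applied without calling the results post hoc.

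**Working it through.** **The protocol's own figure.** The only sample-size figure is in section 7.8: a 90% exact interval of (.56, 1) if 4 of 4 participants complete. The exact lower limit when all n succeed is a^(1/n). With a = 0.10, 0.10^(1/4) = 0.562, which matches. With a = 0.05 (equal-tailed two-sided 90%), 0.05^(1/4) = 0.473, which does not. The figure is therefore a one-sided 90% bound. It concerns completion and says nothing about precision for language.

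**What estimation would give.** Inputs: planned n = 20 (protocol section 4.1); analysed n not stated, so a range is assumed. Let D be each participant's active-minus-sham change, and express results in units of the SD of D.

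- Half-width of the 95% interval for mean D: t(0.975, n-1)/√n. At n=4: 3.182/2 = 1.59.
- 95% limits for the SD, as multiples of the observed SD: √[(n-1)/χ²(0.975, n-1)] and √[(n-1)/χ²(0.025, n-1)].
- Smallest two-sided p from an exact sign-flip or signed-rank test across participants: 2 × 0.5^n. At n=5: 0.0625.

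| n | Half-width (SD) | SD limits (× observed) | Smallest exact p |
|---|---|---|---|
| 3 | 2.48 | 0.52–6.28 | 0.25 |
| 4 | 1.59 | 0.57–3.73 | 0.125 |
| 5 | 1.24 | 0.60–2.87 | 0.0625 |
| 6 | 1.05 | 0.62–2.45 | 0.031 |
| 8 | 0.84 | 0.66–2.04 | 0.008 |
| 10 | 0.72 | 0.69–1.83 | 0.002 |
| 20 | 0.47 | 0.76–1.46 | <0.0001 |

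Estimation is possible on every row. An exact group test cannot reach 0.05 on the first three. A paired t-test has no such floor, but relies on a normality assumption that so few values cannot check.

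**Period.** D equals the treatment effect plus the period difference in one sequence, and minus it in the other. The raw mean therefore retains a fraction (n₁ - n₂)/n of the period difference, where n₁ and n₂ are the sequence sizes. This is zero only if the sequences are equal in size. Adjusting for period leaves n-2 degrees of freedom; with equal sequences the n=4 half-width becomes 4.303/2 = 2.15 SD.

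**Does the Wilcoxon test fill the gap?** Its unit is unclear: items, tests or participants. Within a participant, it gives no between-participant variance. Across participants, it sits badly with the statement that group analysis was precluded, and cannot reach 0.05 at n of 5 or fewer. On either reading the SAP attaches no estimate, SD or interval to it.

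**The case against.** Much of the case for the SAP stands. The protocol summary makes ANOVA testing depend on sample size, so omitting the group test is no departure. The SAP discloses the change and its reason in its opening lines, and corrects the McNemar comparisons for multiplicity, though not the Cochran's Q tests that lead to them.

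The composite is also less ready to use than it looks. Section 6.3 speaks of seven scores without listing them. Section 5.4.4 has nine headings; leaving out the MoCA and the trained tasks would give seven, but sections 4.1 and 5.1 count trained tasks within the battery. Several tests yield more than one score, and naming and speech have alternative instruments. The Z-scores are scaled to the study's own subjects, so at very small n the scale is itself unstable. The SAP's worry about carryover and progression is a fair criticism of a raw active-minus-sham mean.

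Restoring the summary would do little for precision. Required sample size scales with the SD squared, so the SD limits span a factor of (2.87/0.60)² ≈ 23 at n=5 and (3.73/0.57)² ≈ 43 at n=4.

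None of this justifies omitting the estimates. The sentence promising them carries no condition on sample size, and a wide interval shows a planner how little is known.

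**Conclusion.** Followed as written, the SAP leaves out a stated product of the pilot, for a reason that limits testing but not estimation. This should be corrected.

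The size depends on an n the documents do not give. At an assumed n of 4 or 5 the mean paired difference would be known to within ±1.59 or ±1.24 SD, against ±0.47 SD at the planned 20. These figures assume roughly normal paired differences and no period adjustment.

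A reader might infer more than the documents support:

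- That the trial cannot deliver these estimates. The SAP computes percentage change under active and sham, and the test scores exist, so the estimates are unplanned rather than out of reach.
- That every group-level estimate has been abandoned. The unit of the Wilcoxon test is unclear, and descriptive summaries are not ruled out.
- That such estimates are the trial's whole purpose. The primary objective is efficacy, and consent and completion rates are also outcomes.
- That the change followed unblinding or served selective emphasis. The SAP shows the sample was known; it does not show who had seen treatment results.

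**What to change.** Amend the SAP to:

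1. State the number of participants analysed, by treatment sequence.
2. State which seven scores enter the composite, including the instrument used where the protocol allows alternatives, and acknowledge any choice made now as post hoc.
3. Report descriptively, for the composite and each test, every participant's active-minus-sham T0-T1 change by sequence, with the mean, SD and 95% intervals for both across participants. Add a period-adjusted version where both sequences have enough participants.
4. State the unit of the Wilcoxon test.
5. Label the Cochran's Q, McNemar and Wilcoxon results post hoc and exploratory.

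No group p-value is needed: at n of 5 or fewer an exact test cannot reach 0.05 two-sided.

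The cost is SAP wording and a short table from data already held. The downside is that the intervals will look very wide, and nothing here repairs imprecision due to a shortfall against 20.

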3. RATIONALE

3.1 Scientific Premise

Aim #1. Evaluate the therapeutic efficacy of HD-tDCS. Anodal (positive) tDCS appears to increase both the amount and the speed of learning by promoting mechanisms of long-term potentiation (Fritsch., 2010). From a behavioral perspective, these changes in synaptic activity seem to outlast the initial period of stimulation only when the stimulation is delivered 'online' during a behavioral training task (Monti et al., 2008; Baker et al., 2010; Marangolo et al., 2013), and when compared to the 'offline' method, only 'online' tDCS was capable of reducing vocal response times in a study of elderly adults (Fertonani., 2014). These findings are in support of a pivotal part of our scientific premise: that 'online' HD-tDCS is preferable in elderly persons with aphasia.

Only a small number of tDCS studies exist in the the PPA population; some excluded the lvPPA subpopulation altogether (Cotelli et al., 2014; Teichmann et al., 2016) and another included lvPPA patients, but with what we believe are relative weaknesses in its design: The use of a conventional tDCS montage without individualized modelling of current delivery, the use of a 'locked' target site without consideration of the specific PPA variant at hand, and a relatively short 2-month "wash out" period as evidenced by the persistence of behavioral gains at the 2-month follow up (Tsapkini et al., 2014). An additional small number of studies that included lvPPA patients have been published, all of them relying on the use of conventional tDCS, a single stimulation target for all PPA subtypes, or the absence of a sham condition for comparison (e.g. McConathey et al., 2017; Hung et al., 2017). Based on the support from the discussed studies our scientific premise is that tDCS when combined with language training interventions can improve language performance in PPA. Nevertheless, what remains unknown are the effects of using 'online' HD-tDCS when tailored to each PPA variant and guided by the individualized modelling of target sites.

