Spontaneous Speech Sample. This task consists of picture description from the Boston Diagnostic Aphasia Examination (“Cookie Theft Picture”), in which the participant is asked to “Tell me everything you see going on in this picture.” Responses will be digitally recorded and later transcribed and analyzed. Since diagnostic criteria for IvPPA includes changes to spontaneous speech, obtaining an objective measure of discourse can detect subtle changes to speech and language that may be clinically meaningful (Ahmed et al., 2012; Wilson et al., 2010). Specifically, through automated analyses we will measure semantic content, speech fluency, and timing measures such as words-per-minute (Ahmed et al., 2013; Mueller et al., 2017).

Estimated testing time: 4 minutes.

Alternatively, we will use the oral production sub-test of the NAB. This sub-test uses a speech output task in which the examinee orally describes a picture of a family scene (Stern & White, 2003). 2 different versions of the family scene will be used (one per treatment condition).

Estimated testing time: 4 minutes.

Reading Comprehension. We will use the reading comprehension sub-test of the NAB. A two-part sub-test that requires the examinee to demonstrate reading comprehension of single words and of sentences by pointing to multiple choice sentences that match the visual stimuli (Stern & White, 2003). 2 different versions of the test will be used (one for each treatment period).

Montreal Cognitive Assessment (MoCA). MoCA is a widely used screening assessment for detecting cognitive impairment. It is a one-page 30-point test administered in approximately 10 minutes (Nasreddine et al. 2005). 3 different versions of the test exist in English, and 2 will be used for each patient (one per treatment condition).

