‘Trained’ tasks. This includes items tested at baseline and after treatment periods, with half of them also practiced (i.e. trained) during all stimulation procedures (either sham or real tDCS). It will include the reading of words and non-words and the repetition of non-words (approximately 480 items, a total of 288 items for reading and 192 for repetition, divided across two treatment periods). Non-word tasks were selected due to their reliance on the kind of phonologic mechanisms subserved by the dominant temporo-parietal cortex and impaired in IvPPA (Pillay et al., 2017). We will test vocal reaction times and the data will be analyzed using a Matlab custom script. Estimated testing time: 25-30 minutes.

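### The SAP specifies no analysis of vocal reaction time, and its right/wrong item tests cannot take reaction times, fluency counts or speech rate

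*SAP*

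**What the plan says.** Protocol section 5.4.4 describes the trained tasks as reading of words and non-words and repetition of non-words. There are about 480 items (288 reading, 192 repetition) divided over the two treatment periods, and half are practised during stimulation. The only measure it names for them is speed: "We will test vocal reaction times and the data will be analyzed using a Matlab custom script". Section 3.1 gives a speed result as part of the case for stimulating during the task: "only 'online' tDCS was capable of reducing vocal response times in a study of elderly adults".

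The same section 5.4.4 includes a fluency test with three letters and two categories, in which the participant generates words freely. It also includes a picture description, for which "we will measure semantic content, speech fluency, and timing measures such as words-per-minute".

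The SAP (Statistical Analysis) has two parts. Within a condition, "The Cochran's Q test was used to determine if there were any differences on a dichotomous variable across the three-trial period timepoints", followed by McNemar tests against baseline. The variable for these tests is binary: "we coded 'right' and 'wrong' answers to an individual assessment item as our dichotomous variable". Between conditions, "we utilized a Wilcoxon-signed rank test to assess participant performance changes between aHD-tDCS and sHD-tDCS", with the example "aHD-tDCS T0-T1 percentage change from baseline vs. sHD-tDCS T0-T1 percentage change from baseline". The significance threshold is common to all: "A p-value of <0.05 was used to describe statistical significance". The SAP does not mention reaction time, the trained tasks, practised versus unpractised items, fluency or the speech sample.

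**The concern.** The trained tasks are the behavioural half of the intervention, because stimulation is given while the participant does them. The protocol says their speed will be tested, but the SAP has no analysis of speed. Tests on right/wrong items respond only to items whose status changes. An item answered correctly at both times adds nothing to them, however much faster the second answer is.

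Fluency counts and words per minute have the same difficulty. They are not answers to a fixed list of items, so the within-condition tests have nothing to work on. If stimulation speeds retrieval or increases spoken output without changing accuracy, the within-condition analysis as written would not show it.

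**Working it through.** The documents give no power or sample-size figure for this point, so there is none to reproduce. The check compares the measures with the tests and then gauges what is lost.

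1. **Items available** (section 5.4.4, assuming an even split over periods). 288/2 = 144 reading and 192/2 = 96 repetition items, so 144 + 96 = 240 per period. Half are practised: 240/2 = 120 practised and 120 unpractised per period.

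2. **What each test can take.** Cochran's Q and McNemar need a 0/1 outcome on the same items at each time. Accuracy on the trained lists fits. Reaction time (continuous), counts of freely generated words, and words per minute do not. The signed-rank test needs paired numbers and could take any of them.

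3. **Sensitivity to a pure speed gain** (simulation, 1,000 runs per setting; all inputs assumed). Responses were 10% faster and accuracy was unchanged at 60%, 80% or 95%, independent across times. On the log scale, item SD was 0.15 and residual SD 0.25. Cochran's Q used three timepoints. The comparator was a signed-rank test on reaction times for items correct at both of two times.

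| Items | Accuracy | Cochran's Q rejects | Reaction-time test rejects |
|---|---|---|---|
| 120 | 60% | 5.3% | 44.0% |
| 120 | 80% | 4.8% | 67.3% |
| 120 | 95% | 5.5% | 83.3% |
| 240 | 60% | 4.6% | 73.7% |
| 240 | 80% | 5.2% | 93.6% |
| 240 | 95% | 5.0% | 98.6% |

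A hand check of the first row agrees. Items correct at both times: 120 × 0.6² = 43.2. Mean log change: ln 0.9 = −0.105. SD of a difference: 0.25 × √2 = 0.354. Then 0.105/0.354 × √43.2 = 1.96, which means power near 50% by the normal approximation, against 44% simulated.

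4. **Whether the Wilcoxon test fills the gap.** The SAP leaves the pairing unit open. The possible units are:
   - *Items.* The SAP says one list was used within a condition. The protocol divides the items over the periods, so active and sham may share no items to pair.
   - *Whole measures.* Each participant has one pair per measure, which cannot support a test.
   - *Fluency prompts.* 3 + 2 = 5 pairs. The smallest exact two-sided p is 2 × 0.5⁵ = 0.0625. With six pairs it would be 2 × 0.5⁶ = 0.031. The large-sample version has mean 5 × 6/4 = 7.5 and variance 5 × 6 × 11/24 = 13.75, so z = 7.5/3.71 = 2.02 and p is about 0.043. The SAP does not say which version was used.
   - *Pooled assessments.* There may be enough pairs, but no single measure gets its own result.

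**The case against.** The strongest reply is that the SAP is silent on these measures and does not exclude them. The binary code belongs to Cochran's Q and McNemar. The Wilcoxon test on percentage change is separate and needs no binary data, so a reader who infers that every assessment is scored right or wrong goes beyond the text. The protocol sends reaction times to a Matlab script while the SAP describes SPSS analyses, so no replacement of speed by accuracy is documented. The gap is also not new: protocol section 6.3 averages seven unlisted Z-scores and sets out no reaction-time model. All of this stands.

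Three further limits also stand. Semantic content of speech could be coded as units present or absent, so the point is firm only for counts, rates and timing. Accuracy on the trained tasks remains testable. And no baseline accuracy is given, so a ceiling effect cannot be asserted, particularly as the non-word tasks were chosen because the function they use is impaired in this disease.

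A reader might also infer that the premise of stimulating during the task goes untested because speed is not analysed. The documents do not support that. Section 3.1 gives a second support, effects that outlast stimulation, which names no reaction time. Active and sham are both given during the tasks, so no analysis of this trial could compare stimulation during the task with stimulation apart from it.

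None of this supplies the missing analysis. The one measure named for the trained tasks has no stated analysis in the SAP.

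**Conclusion.** The concern holds as an omission that should be repaired. The SAP specifies no analysis of vocal reaction time, and its within-condition tests cannot take reaction times, fluency counts or words per minute. The Wilcoxon test could take them, but its measures and pairing unit are not stated. It would be too strong to say that these measures can produce no result, since pooled pairs or a large-sample p are not ruled out.

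The size of the loss depends on assumed inputs. With responses 10% faster and accuracy unchanged, the right/wrong test rejects at about its 5% error rate, while a reaction-time test rejects in 44–99% of runs over the settings shown. Those figures rest on the assumed SDs and accuracy range and on independence across times; the documents give none of these. The 120 and 240 item counts assume an even split. The limit of 0.0625 for five fluency prompts is exact arithmetic and needs no such assumption.

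**What to change.** Add to the SAP, for each participant and condition, a paired item-level analysis of log reaction time on the trained tasks. It would run from T0 to T1 and from T0 to the third timepoint (T2), on items correct at both times. Analyse practised and unpractised items separately (about 120 each per period), because pooling them would dilute a training-linked effect. Show accuracy alongside, so that a trade of speed for accuracy is visible, and report the active-minus-sham difference in mean log change, signed so that faster is better.

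Report fluency counts and words per minute as raw changes by condition with the active-minus-sham difference, outside the right/wrong tests. State which measures enter the Wilcoxon test, what forms a pair, and whether the p-value is exact.

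The cost is SAP wording and processing of data the protocol already plans to collect. There are three downsides to state:

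- Keeping only correct responses selects on something measured after treatment, and the retained items can differ between active and sham. Showing accuracy exposes this but does not remove it.
- Within one participant, the active-minus-sham difference also carries any difference between periods and item lists, so it is descriptive.
- The SAP was written with the small sample already known, so the added results must be labelled post hoc.
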